9. DATA COLLECTION

All data collection will be prospective and will be collected after the patient has voluntarily agreed to participate in the study by signing and dating an IRB-approved informed Consent and HIPAA document (as required by the local IRB). Data will be collected according to the scheme outlined in Table 1.

a. **Methods:**

- i. Data can be collected via paper form, or entered directly to an online database, if applicable.
- ii. If the site has an existing database, data may be sent to OrthoSensor via raw data format in an excel spreadsheet. If using a local database, it must be ensured that the data in the spreadsheet is compliant with the methods presented in the case report forms, as all data must be available for statistical analysis.

b. **Data and Clinical Assessments:**

- Patient Demographics: Age at surgery, gender, surgical side, height, weight, primary diagnosis. This data is collected from the medical record.
- Operative Data: Part Numbers (if able) or Femoral Component Type & size, Tibial Tray Type & Size, Tibial Bearing Type & Size, Patella Type & Size, OR Time, Surgical Technique, Surgical Approach, Operative Complications, Length of stay. This data is collected from the medical record.
- Length of stay, Discharge Destination: Based on the operation day and day of discharge, the length of hospital stay is determined.
- Patient Reported Outcome Measures – Perceived functioning, including pain, satisfaction and function will be measured using three patient reported outcome measures (PROMs).

- **EQ-5D**
A standardized instrument for use as a measure of health outcome
- **Knee Society Score (2011 Version)**
The latest version of the KSS was developed in 2011 and introduced by the Knee Society. The latest version of the KSS originates from the popular KSS (from 1989); both physician and patient derived. It includes versions administered preoperatively and postoperatively. It has an initial assessment of demographic details, including an expanded Charnley functional classification. The objective knee score, completed by the surgeon, includes a VAS score of pain, walking on level ground and on stairs or inclines, as well as an assessment of alignment, ligament stability and ROM, along with deductions for flexion contracture or extension lag. Patients then record their satisfaction, functional activities, and expectations. Given the diverse activity profiles of many contemporary patients, the functional component of the score was improved to include a patient-specific survey, which evaluates features such as standard activities of daily living, patient-specific sports and recreational activities, patient satisfaction, and patient expectations. The new Knee Society Knee Scoring System has been developed and validated, in part, to better characterize the expectations, satisfaction, and physical activities of the younger and more diverse population of current patients undergoing TKA. The score was validated in a thoughtful and methodical fashion confirming internal reliability and analyzed for differential item functioning. The new Knee Society Scoring System is broadly applicable across sex, age, activity level, and implant type. Completing the questionnaire takes 10 to 30 minutes.
- **Forgotten Joint Score (FJS)**
The FJS is a patient reported outcome measure, consisting of 12 questions (e.g. awareness traveling in a car or climbing stairs?). It uses a 5-point Likert response format and the raw score is transformed to range from 0-100 points. High score indicates good outcome, e.g. a high degree of forgetting the joint in everyday life (forgotten joint phenomenon). The FJS has a low ceiling effect and was designed to discriminate between good, very good and excellent outcomes after TKA.
- **Knee Pain Evaluation Form**
The knee pain evaluation will be used to assess the prevalence and location site of knee pain when applicable. This evaluation will be completed by the investigator post total knee surgery during the intervals defined in Table 1 “Schedule of study assessments”.
- Radiographic evaluation via Mediolateral and anteroposterior x-rays as is standard of care. The prevalence and location of radiolucency and/or osteolysis is evaluated on both AP and lateral views at each patient’s routine postoperative

follow-up visits. These evaluations are performed by each patient's operating surgeon.

- Complications, adverse events, and survivorship data will be collected and reported. This information will be gathered at each of the study follow-up visits.

c. Data Collection Periods:

Data will be collected pre-operatively, intra-operatively, and post-operatively at 6 weeks, 6 months, and 1 year. All time point windows are determined using the date of surgery (DOS) as day 0, including all annual visits. The visit windows are as follows:

Pre-operative: within 3 months prior to the date of the surgery excluding

*Pre-operative radiographs. Pre-operative radiographs taken within 12 months of scheduled knee replacement surgery are sufficient.

Intra-operative: within 2 weeks after the date of surgery

6 weeks: DOS + 6 weeks ± 4 weeks

6 months: DOS + 6 months ± 45 days

1 year: DOS + 1 year ± 90 days

2 year: DOS + 2 year ± 90 days

Table 1. Schedule of study assessments

Data Collected	Pre-op Baseline	Operative Discharge	6 Weeks	6 Months	1 Year	2 Years
Obtain Written Informed Consent	X					
Demographics	X					
Intra Operative		X				
EQ-5D	X		X	X	X	X
New-KSS	X		X	X	X	X
FJS			X	X	X	X
Knee Pain Evaluation Form				X	X	X
Radiographic Alignment	X		X	X	X	X
Adverse Event Reporting (When Present)		(X)	(X)	(X)	(X)	(X)

10. Analysis to be Performed on Data (e.g. Statistical Analysis)

Analysis of the data will be performed using SPSS version 21. Comparative Statistics will be run between outcomes data stratified by both groups: Analysis of variance (AVOVA) will be used to assess the difference between each group, with post-hoc t-tests to demonstrate significance. Separate analyses will be performed to evaluate power of sample sizes and any correlative affect that demographic/clinical variables may have on patient outcomes.

11. Monitoring of data collection

The Sponsor will monitor all data collected for accuracy and completion. The site will be monitored at least once per calendar year following the initial/first-monitoring visit.

12. Patient Identification

Each patient who signs an informed consent document will be given a unique, sequential 3-digit number. The three initials of each patient will be used (first, middle, last). In the case where the subject does not have a middle initial, that placeholder will be held by a dashed line (-). This unique patient identifier will be used on all study-related documentation for each subject enrolled in the study. The patient's initials will be used to further identify the subject; no names will be used.

13. Screening Enrollment Logs

A record of all patients consented for the study, with their consecutively assigned study numbers, will be maintained in the site's Regulatory Binder. This log will be identified as the Screening/Enrollment Log. Patients who sign a consent form but who do not continue into the study for whatever reason (i.e., cancel surgery) will be assigned a unique subject identifier which **WILL NOT BE REASSIGNED** to anyone else.

14. Patient Identification

Each patient who signs an informed consent document will be given a unique, sequential 3-digit number. The three initials of each patient will be used (first, middle, last). In the case where the subject does not have a middle initial, that placeholder will be held by a dashed line (-). This unique patient identifier will be used on all study-related documentation for each subject enrolled in the study. The patient's initials will be used to further identify the subject; no names will be used.

Example: Subject number: 001.

Subject initials: FML where F = first initial, M = middle initial, L = last initial. This subject's unique identifier would be 001 and uniquely associated with the initials FML.

15. Institutional Review Board Approval and the Informed Consent Document.

It is the responsibility of the Principal Investigator to ensure that an Institutional Review Board (IRB) reviews the study and that the IRB acts in accordance with the requirements set forth in 21CFR56 – Institutional Review Boards. The Principal Investigator will forward copies of the protocol and all required documents to the IRB for review. Further, it is the Principal Investigator's responsibility to promptly inform the IRB of any revisions to the Clinical Study Protocol, to promptly report any serious medical device adverse events and/or unexpected events and to provide a periodic report of the study's progress to the IRB at intervals not to exceed 1 year. Any proposed amendment to the protocol that involves increased risk to the subject will require IRB approval prior to its enactment.

The investigator must forward written verification of the initial IRB review and approval to OrthoSensor before beginning the clinical study. The Principal Investigator must immediately forward copies of all subsequent correspondence between the Principal Investigator and the IRB concerning the continued approval of this clinical study, or withdrawal of such approval, to OrthoSensor.

16. Administrative Considerations

- **Ethics: The Declaration of Helsinki**

In any research on human subjects, each potential subject must be adequately informed of the aims, methods, anticipated benefits and potential hazards of the study and the discomfort it may entail. He or she should be informed that he or she is at liberty to abstain from participation in the study and that he or she is free to withdraw his or her consent to participation at any time. (21CFR312.120(3)I.9.

- **Changes to the protocol**

OrthoSensor and the Investigator must approve any changes made to this Protocol and/or any of the appendices and are subject to the approval of the relevant Institutional Review Board(s).

- **Clinical Investigator Agreement**

The Clinical Investigator Agreement is a written agreement to be signed by the Investigator that defines his/her responsibilities and willingness to follow the study protocol. This agreement must be signed by the Investigator and submitted to OrthoSensor before the initiation of the study.

- **Completion of the Study**

OrthoSensor will notify the Investigator when adequate data have been collected or when the clinical evaluation is terminated for any reason.

- **Reporting of Results**

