1. INTRODUCTION

The success of total knee arthroplasty (TKA) depends on a multitude of surgical factors, including appropriate rotational alignment of the prosthetic components [11]. Despite the high success rate of TKA, early post-operative complications can occur as a result of poor rotational positioning of one or both components [5, 8, 18], which may ultimately require revision surgery [11, 13]. Complications indicative of tibiofemoral rotational incongruity may present early in the post-operative period with patient complaints of anterior knee pain, joint stiffness, the sensation of instability, and difficulty navigating stairs and inclined planes. It has been reported that the incidence of anterior knee pain may be as high as 20% after a TKA [1, 10, 14]. Clinical examinations of these incongruent patients can reveal restricted range of motion, patellar crepitus, patellar maltracking (tilt - dislocation), and significant rotational mismatch displayed by rotational gait disturbances (foot progression angle) [3, 4, 6, 14, 16-18]. Suboptimal outcomes due to incongruity, which have been well documented in literature, may be associated with only small rotational deviations of the tibial and femoral components. For instance, Barrack, et al. reported that as little as 6.2° of internal rotation (IR) of the tibial component is associated with postoperative anterior knee pain [1]. Berger, et al. showed that combined IR of the tibial and femoral components from 3° to 8° was correlated with patellar subluxation, and 7° to 17° of combined IR correlated with observed patellar dislocation or patellar prosthesis failure [2].

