3. OBJECTIVES

The objectives of the study are twofold: 1) Evaluate how intra-operative sensing may assist the surgeon with tibiofemoral rotational alignment by testing the precision and variability of setting tray rotation to the mid-third of the tibial tubercle. 2) Understand if patients with a combined axial rotation couple at the tibiofemoral joint and quantitative intercompartmental balance, achieved with the use of VERASENSE, exhibit less post-operative knee pain and improved clinical outcomes. Radiographic outcomes will also be assessed to measure post-operative alignment and to evaluate the prevalence and location of radiolucency and/or osteolysis.

Hypothesis: TKA with VERASENSE results in a more reliable and precise option for establishing implant-to-implant congruency and joint balance leading to less knee pain, faster return to normal activities and higher patient satisfaction compared to TKA without VERASENSE.

The secondary objectives of the study are to establish correlations between the intraoperative VERASENSE data, the surgeon's perception of balance and patient outcomes in addition to understanding any learning curve associated with using new technology.

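### No pain-severity analysis is designated: the only severity scale described sits inside the surgeon-completed KSS objective score and should be analysed on its own, adjusted for its pre-operative value

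*Combined protocol and SAP*

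**What the plan says.** Section 3 (Objectives) asks whether patients treated with the sensor "exhibit less post-operative knee pain and improved clinical outcomes". The hypothesis there expects better congruency and balance, "leading to less knee pain, faster return to normal activities and higher patient satisfaction". Neither statement names a pain scale, a visit or a measure.

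Section 9b describes the 2011 KSS in two parts. The first is introduced as "The objective knee score, completed by the surgeon"; it "includes a VAS score of pain, walking on level ground and on stairs or inclines, as well as an assessment of alignment, ligament stability" and range of motion, with deductions for contracture or lag. The second is the patient's part: "Patients then record their satisfaction, functional activities, and expectations". Pain is not listed in the second part. Section 9b also describes a Knee Pain Evaluation Form, completed by the investigator, for the prevalence and site of pain.

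Table 1 schedules the KSS before surgery and at 6 weeks, 6 months, 1 year and 2 years. It schedules the pain form at 6 months, 1 year and 2 years only.

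On analysis, Section 10 says "Comparative Statistics will be run between outcomes data stratified by both groups", using ANOVA with post-hoc t-tests. It names no instrument, subscale, item or visit, and no adjustment of the group comparison for baseline.

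**The concern.** Pain is the first clinical benefit claimed, and the plan does not say how its severity will be compared. The one severity scale described is bundled with components close to what the sensor guides: Section 5 says Group B uses the device to guide rotational alignment and balance, and the objective score grades alignment and ligament stability. If that score were later cited on the pain question, it could rise in Group B with no change in pain, or stay flat despite a real pain benefit.

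The trial already collects what a cleaner comparison needs. Section 1 lists anterior knee pain and "difficulty navigating stairs and inclined planes" among the complaints that suggest rotational incongruity. The stairs/inclines VAS is the closest recorded match, and it is due before surgery and at every follow-up visit.

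**Working it through.** **1. What each instrument can say about pain, as described**

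| Instrument | Pain content described | Completed by | Pre-op | 6 wk | 6 mo | 1 yr | 2 yr |
|---|---|---|---|---|---|---|---|
| KSS objective score | VAS severity, with alignment, stability, ROM, deductions | Surgeon | X | X | X | X | X |
| KSS patient part | None listed | Patient | X | X | X | X | X |
| Knee Pain Evaluation Form | Prevalence and site | Investigator | – | – | X | X | X |
| EQ-5D | Items not described | PROM | X | X | X | X | X |
| Forgotten Joint Score | Joint awareness | Patient | – | X | X | X | X |

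I read the VAS sentence as two items, level walking and stairs or inclines. That is reasonable, but the sentence is ambiguous. On this reading the VAS is the only described measure of pain severity, and it has a pre-operative value.

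**2. The plan's own figure.** There is none to reproduce. About 500 patients (250 per group) is stated without alpha, power, effect size or SD.

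**3. Illustration: what would happen if the objective total stood in for pain.** Assumptions, none from the documents: two-sided 5%, all 250 per arm analysed, four standardized domains (pain, alignment, stability, ROM), common correlation r, deductions ignored. With weights w, the composite effect is Σ(w·d) / √[Σw² + 2rΣ(wᵢwⱼ)], where the last sum runs over pairs of domains. Power comes from the noncentral t with 498 df and noncentrality d√(250/2).

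- Pain item alone, d = 0.30: noncentrality 0.30 × 11.18 = 3.354, power 92%.
- Equal weights: the SD is √(4 + 12r), which is 2.000 at r = 0 and 2.757 at r = 0.3.
  - Effect on pain only: 0.30/2 = 0.15 SD, power 39%; 0.30/2.757 = 0.109 SD, power 23%.
  - No pain effect, 0.30 in two other domains: 0.60/2 = 0.30 SD, 92% chance of a significant total; 0.60/2.757 = 0.218 SD, 68%.
- Pain carrying half the weight (3:1:1:1): the SD is √12 = 3.464 at r = 0 and √19.2 = 4.382 at r = 0.3.
  - Effect on pain only: 0.90/3.464 = 0.260 SD, power 83%; 0.90/4.382 = 0.205 SD, power 63%.
  - No pain effect, 0.30 in two other domains: 0.60/3.464 = 0.173 SD, 49%; 0.60/4.382 = 0.137 SD, 33%.

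The loss of power depends heavily on the unknown weights. The chance of a significant total with no pain effect stays well above 5% throughout.

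**4. The prevalence route.** Section 1 puts anterior knee pain after TKA as high as 20%. Take that as the control rate, with 250 per arm and power = Φ{[|p₁−p₂|√n − 1.96√(2p̄(1−p̄))] / √(p₁(1−p₁)+p₂(1−p₂))}.

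- 20% against 15%: (0.791 − 1.053)/0.536 = −0.49, power 31%.
- 20% against 11%: (1.423 − 1.003)/0.508 = 0.83, power 80%.

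The form can therefore detect a large fall in prevalence, but it is weak for a fall of five points.

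**5. Baseline adjustment.** ANCOVA multiplies the variance of the group difference by about (1 − ρ²), where ρ is the correlation between the pre- and post-operative item. The documents give no ρ, so I put no figure on the gain. The cost is one of 498 residual degrees of freedom.

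**The case against.** A reader might infer from Section 9b that the pain hypothesis is to be tested on the objective total, or that the VAS items will go unused. The documents support neither. Section 10 speaks only of outcomes data. The VAS is recorded outcome data, and Section 9a requires all data to be available for analysis. The power figures above thus describe a possible misuse, not the plan.

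Nor is severity the only way to address pain. Section 3 does not specify severity, and the one pain figure in the rationale is an incidence. Prevalence on the Knee Pain Evaluation Form is a legitimate, non-composite test, and a randomized post-operative comparison does not need a baseline to be valid. Section 9b also says that pain is measured through three patient-reported instruments. EQ-5D items are not described, so the documents cannot settle whether it grades pain.

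The weights are unknown. Section 9b does not say which alignment the KSS grades, whereas the sensor guides rotation and balance, so the overlap is likely rather than proved. Finally, moving to the VAS items does not remove the problem that the surgeon completes the score.

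All of this stands, and it limits the point. It does not supply a severity analysis, use the pre-operative VAS, or prevent the objective score from being cited on pain. Section 10 does foresee separate analyses of how demographic and clinical variables relate to outcomes, but that is not an adjusted comparison of the groups.

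**Conclusion.** The point holds in a limited form. The pain hypothesis has no designated severity analysis; the only severity scale described is embedded in a surgeon-completed score beside alignment, stability and ROM; and the stated method leaves its pre-operative value unused. A difference in the objective score, in either direction, should not be read as a difference in pain.

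The size cannot be fixed from the documents. Under the assumed weights and correlations, a 0.30 SD pain effect with 92% power on the item would have 23% to 83% power on the total. Gains of 0.30 SD in two other domains alone would make the total significant in 33% to 92% of trials. These ranges matter only if someone uses the total for the pain claim. The prevalence comparison remains available, limited to 6 months onward and to presence and site. This is a worthwhile improvement to the analysis plan, not a defect that invalidates the trial.

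**What to change.** In Section 10:

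- Analyse the KSS pain VAS items separately from the objective knee score, each by ANCOVA adjusting for the same item before surgery.
- Name one primary visit, and name one item as the main pain-severity measure. Stairs/inclines is a natural candidate because it matches the symptom setting in Section 1. Treat the other item as supportive.
- Report pain prevalence from the Knee Pain Evaluation Form alongside, at the visits where it is collected.
- Report the objective knee score as its own outcome, and state that it is not evidence on pain.
- State as a limitation that the surgeon completes the objective score and that Group B surgeons operate using the sensor data. Section 9b calls the KSS a patient-reported measure, so clarify whether the patient marks the VAS directly.

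The cost is a few lines of text and one or two models on data already scheduled, with no new visit or form. The small downside is one or two more tested outcomes to count in any multiplicity rule.

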2. STUDY DESIGN

The study is designed as a prospective, randomized (two-cohort) double-blinded clinical evaluation and will be conducted at multiple centers throughout the United States. Approximately 500 patients will be included and followed for a period of 2 years. Clinical Assessments will be performed at baseline, 6 weeks, 6 months, 1 and 2 years after surgery.

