5. METHODS / PROCEDURES

Patients indicated for TKA and who meet all study eligibility criteria will be asked to participate in the study. Eligible patients will receive a primary unilateral PCL-retaining or – sacrificing TKA using the Stryker Triathlon Total Knee System *with* or *without* the use of the VERASENSE™ Knee System. Patients will be enrolled in a consecutive series consisting of two cohorts (Groups A and B). Both groups are described below:

Group A – Control (Surgeon-Guided) will consist of **250** consecutive patients who will undergo primary unilateral PCL-retaining or – sacrificing TKA using the Stryker Triathlon Total Knee System *without* the use of VERASENSE to guide rotational alignment and balance. **Prior to closing the arthrotomy, VERASENSE will be utilized in a surgeon-blinded fashion to record rotational alignment and intercompartmental pressures through a range of motion.**

Group B (Sensor-Guided) will consist of **250** consecutive patients who will undergo primary unilateral PCL-retaining or – sacrificing TKA using the Stryker Triathlon Total Knee System *with* the use of VERASENSE to guide rotational alignment and balance. The sensor data will be used for balancing per the VERASENSE protocol below.

Each patient will be given a unique study number once informed consent has been obtained. The investigator will be blinded to the patient study number and the patient will be blinded to his/her assigned group. It will be important that all patients remain blinded to their assigned group. The patient will be informed during the consent process that they may or may not receive their knee replacement procedure using the VERASENSE Knee System.

Radiographic outcomes will be assessed on all patients within the first 12 weeks and at the annual visits. Any postop complications will also be monitored.

Surgical Protocol – Using VERASENSE

All knees will be prepared using standard instrumentation and a measured resection or gap balancing technique. The following steps will be performed when using VERASENSE:

Step 1: Establish Tibial Tray Rotation:

Select and position appropriate sized trial tibial tray. Align the tray to the anatomy (mid-medial third of the tubercle) as recommended by the manufacturer's surgical technique. Insert a single anterior or posterior pin (medially or laterally) into the trial tray to allow for internal / external rotational adjustment while maintaining optimal medial / lateral coverage.

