6. CLINICAL SITES

This study will be conducted at multiple centers by experienced, high-volume surgeons in the United States

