7. PATIENT SELECTION

Enrollment: Approximately 500 patients will be enrolled and followed for a period of 24 months in order to assess patient outcomes. Each center is expected to enroll approximately 100 patients (50 in each group). The investigator is responsible for evaluating each patient against the following criteria and assuring that the patient meets the following requirements in order to be enrolled in the study. Each patient must meet all the inclusion criteria and none of the exclusion criteria to be considered for enrollment.

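### Section 7 expects both groups in equal numbers at each centre, but the Section 10 comparison has no centre term, so the test is somewhat conservative and gives up a little power

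*Combined protocol and SAP*

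**What the plan says.** Section 2 describes a "prospective, randomized (two-cohort) double-blinded clinical evaluation and will be conducted at multiple centers". Section 5 plans 250 patients in each of Groups A and B. Section 7 sets the expected layout by site: "Each center is expected to enroll approximately 100 patients (50 in each group". Treatment is therefore meant to be crossed with centre. No section describes allocation stratified or blocked by centre or surgeon.

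Section 6 adds: "This study will be conducted at multiple centers by experienced, high-volume surgeons in the United States". The number of surgeons is not given.

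For the analysis, Section 10 says "Comparative Statistics will be run between outcomes data stratified by both groups". The strata here are the treatment groups. The method is ANOVA for the group difference, followed by t-tests. Demographic and clinical variables appear only in a separate correlative analysis, and neither centre nor surgeon is named there.

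The operative data in Section 9b include surgical technique and approach, but no surgeon identifier.

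**The concern.** The sensor acts through the surgeon, so differences between operators are a plausible source of variation. Section 5 leaves room for them: "All knees will be prepared using standard instrumentation and a measured resection or gap balancing technique", and the PCL may be retained or sacrificed. Some outcomes are also rated by the treating side. Section 9b says of the Knee Society Score: "The objective knee score, completed by the surgeon". It also has the investigator complete the knee pain form and the operating surgeon read the radiographs for radiolucency and osteolysis.

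If outcomes differ between centres and each centre contributes equally to both groups, those differences cancel out of the treatment difference. A group-only ANOVA nevertheless counts them as noise, so the layout expected in Section 7 buys precision that Section 10 does not use. If the split drifts from 50:50, part of the centre differences passes into the estimated effect of that one trial. The plan also includes no look at whether an effect is similar from centre to centre.

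**Working it through.** **Layout, from the documents.** 250 + 250 = 500. At about 100 per centre, 500/100 = 5 centres, and 5 × 50 = 250 per group. The stated numbers agree with each other. The documents give no alpha, power, effect size, SD or ICC, so 500 cannot be re-derived as a powered sample size.

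**Assumptions for illustration.** Two-sided alpha 0.05; total SD = 1; no dropout; ICC (share of outcome variance lying between centres) 0.01 to 0.20; true difference 0.25 SD for the power figures.

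**Split kept at 50:50 in each centre.** The true SE of the difference is sqrt(1 − ICC) × sqrt(2/250). The group-only test uses about sqrt(2/250) = 0.0894. Hence:

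- SE overstatement = 1/sqrt(1 − ICC)
- actual level = 2 × [1 − Φ(1.96/sqrt(1 − ICC))]
- power without centre = Φ((0.25/0.0894 − 1.96)/sqrt(1 − ICC))
- power with centre = Φ(0.25/(0.0894 × sqrt(1 − ICC)) − 1.96)

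| ICC | SE too large by | Actual level | Power without centre | Power with centre | Loss (points) |
|---|---|---|---|---|---|
| 0.01 | 0.5% | 4.9% | 79.9% | 80.2% | 0.3 |
| 0.05 | 2.6% | 4.4% | 80.4% | 81.8% | 1.4 |
| 0.10 | 5.4% | 3.9% | 81.1% | 83.8% | 2.7 |
| 0.15 | 8.5% | 3.4% | 81.8% | 85.8% | 4.0 to 4.1 |
| 0.20 | 11.8% | 2.8% | not run | not run | not run |

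A simulation of five centres of 100 (10,000 runs) gave levels of 4.4% at ICC 0.05 and 4.1% at ICC 0.10, close to the formula.

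**Split not kept.** The shift in the pooled difference is the sum over centres of (nB − nA)/250 × that centre's deviation from the average. Suppose two centres lie 0.5 SD apart:

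- 60:40 in one and 40:60 in the other: 20/250 × 0.5 = 0.04 SD.
- 70:30 and 30:70: 40/250 × 0.5 = 0.08 SD, about a third of 0.25 SD.
- Exact 50:50 everywhere: zero.

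An aligned worst case shows how far this could go. Take four of the five centres at 60:40 or 40:60, each lying 5 points from the average, with every imbalance pushing the same way: 4 × (20/250) × 5 = 1.6 points. Under simple randomisation of 100 patients, nB − nA has SD 10, so the shift from each centre has SD 10/250 × 5 = 0.2 points. Over four centres this is sqrt(4) × 0.2 = 0.4 points, so 1.6 points is a 4-SD event.

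Simulated type I error under simple randomisation without a centre term was 4.9% (ICC 0.05) and 5.1% (ICC 0.10). The unadjusted SE already allows for chance imbalance.

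**The case against.** The strongest reply is that nothing here endangers validity. If the split holds, the error is on the safe side. If it does not hold but randomisation is sound, the test keeps its level. A reader might infer that leaving centre out biases the treatment effect or inflates false positives; the documents do not support that. Bias would need systematic imbalance, which is a matter of how patients are allocated and not of a missing model term. What stands on the other side is that the 50:50 split is only expected and approximate, and that no described method secures it.

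The size of the operator effect is also unknown. The documents specify one implant system, a written sensor protocol and experienced surgeons, and several outcomes (EQ-5D, Forgotten Joint Score, the patient parts of the Knee Society Score) are not rated by the surgeon. A large ICC cannot be presumed, so the range has to start low; at 0.01 the loss is negligible.

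A reader might also infer that the trial cannot show whether an effect holds across operators. That goes too far. Data come from the sites and enrolment logs are kept by site, so centre can probably be recovered, and surgical technique and approach are recorded. The supportable statement is that a by-centre analysis is not planned, and that the surgeon within a centre is not shown to be captured.

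**Conclusion.** The point holds as one of efficiency and reporting. The design expects groups balanced within centre, and the analysis does not use that balance. The cost ranges from almost nothing to a modest loss of precision and power, as tabulated, and depends on an ICC that the documents do not give and on the split being roughly kept. Chance departures from the split move a single estimate without bias on average; the 1.6-point figure is a worst case and should not be read as an expected bias. Protection against systematic imbalance is not described. This is a cheap improvement; the omission does not invalidate the comparison.

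**What to change.** In Section 10, replace the group-only ANOVA with a model containing group and centre, or group and surgeon where a centre has several. Report the group difference by centre descriptively. A centre term also removes the shift caused by unequal splits between centres, though not any selection of patients within a centre.

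In Section 9b, add a surgeon identifier to the operative data. The learning-curve objective in Section 3 needs it as well.

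If enrolment is still open, state in Sections 5 and 7 that allocation is made within centre, so that the 50:50 split is delivered and not just expected.

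The cost is about 4 degrees of freedom for five centres (498 falls to 494), more if surgeon is used; one case report form field; and a protocol amendment, which under Section 16 needs sponsor, investigator and IRB approval. Allocating within centre also changes the randomisation scheme. No extra patients or procedures are needed.
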